• If Yes: Outcome of pregnancy (it should be possible to enter more than one date, should there be more than one pregnancy during follow-up):

- Ongoing pregnancy
- Miscarriage; date: ...
- o Ectopic; date: ...
- o Termination; date: ...
- o Delivery; date: ...
- Complications from the lesion during pregnancy? No/Yes (pop up list):
 - Acute pain
 - Chronic pain
 - Suspected torsion
 - Infection
 - Haemorrhage related to the cyst
 - Cyst rupture
 - Required surgery
 - Other, please specify:
- Complications from the lesion during delivery? No/Yes (pop up list):
 - Acute pain
 - Suspected torsion
 - Haemorrhage
 - Cyst rupture
 - Obstructed labour
 - Malpresentation (e.g. breech or unstable lie)
 - Other, please specify:

Ultrasound examination

A standardized ultrasound examination following the IOTA protocol is carried out.

All ultrasound variables are included in the dedicated software. In the database 0 always means NO and 1 always means YES.

The adnexal lesion is that part of an ovary or of an adnexal mass that is judged by ultrasonography to be not consistent with normal physiology. This can be a persistent unilocular cyst, surrounded by normal looking ovarian stroma with some follicles. In this case the whole ovary containing the cyst is the 'ovary', whereas the unilocular cyst is the 'lesion'. Both are measured and the cyst is described as being 'unilocular' and not 'unilocular-solid'. In other cases the lesion is separate from the ovary (e.g. hydrosalpinx). Again, both ovary and lesion are measured separately. In other cases no normal ovarian stroma is seen. In these cases the lesion and the ovary are undistinguishable and the measurement of lesion and ovary will be the same.

Measurements (in mm): The ovary in two perpendicular planes

The lesion in two perpendicular planes

The volume of the tumor is calculated from the three diameters in two perpendicular planes

• The presence of ascites (*i.e.fluid outside* the pouch of Douglas) is noted (yes/no).

• Fluid in the pouch of Douglas is measured in the sagittal plane (the largest anteroposterior diameter is given).

- An incomplete septum (as seen in hydrosalpinges) is defined as a thin strand of tissue running across the cyst cavity from one internal surface to the contralateral side, butis not complete in some scanning planes. If a cyst only has incomplete septa, it is unilocular, despite the fact that in certain sections the cyst appears to be multilocular.

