All centres will receive the **IOTA 5 study screen**. At initial set up centres can choose between the two options:

- 1. Full IOTA 5 study (with planning of appropriate follow up and conservative management whenever feasible).
- 2. Observational study only (e.g. in radiology departments that are not involved in management decisions)

Recorded variables (entered in the astraia study screen).

Patient data

(click one option from list below)

- > New patient with diagnosis of adnexal mass
- ➢ New patient who was already in follow up in your centre for adnexal mass before she was enrolled to the IOTA 5 study. How many months in follow up? ...
- > Follow up scan of patient that is already enrolled to the IOTA 5 study before

Ultrasound

- Spontaneous resolution of the adnexal mass (no further details are entered)
- Adnexal mass present (fill in all variables below)
- 12 variables described in LR 1:
 - o Age
 - o personal history of ovarian cancer
 - o personal history of breast cancer
 - Max diameter of lesion
 - Max diameter of solid component
 - o Presence of ascites
 - o Presence of blood flow within papillary projection
 - o Irregular internal cyst walls
 - Presence of a purely solid tumour
 - Colour score (1/2/3/4)
 - Presence of acoustic shadows
 - Current hormonal therapy
 - Presence of pain during the examination
- as well as simple rules, RMI and other variables:
 - Type of tumour (unilocular/unilocular-solid/multilocular /multiloc-solid/solid)
 - Ovarian crescent sign
 - Cyst content
 - o Incomplete septum
 - o Mobility: mobile/reduced mobility/completely fixed
 - Number of locules
 - \circ Number of papillations (0/1/2/3/more)
 - Size of ovary
 - o Bilateral tumour
 - Evidence of metastases
 - Menopausal status: premenopausal/postmenopausal

- Serum CA 125 result (not mandatory)
- Symptoms during the last year before ultrasound scan (multiple options are possible)
 - Pelvic pain
 - Postmenopausal bleeding
 - o increased abdominal size
 - o persistent abdominal distention (bloating)
 - \circ appetite loss
 - \circ constipation
 - o diarrhoea
 - o urinary urgency
 - o urinary frequency
 - o weight changes
 - o dyspareunia
 - Other: please specify:
- For centres participating at the full IOTA 5 study only: Suggested management recorded by examiner: "What type of management do you propose for this patient based on ultrasound and clinical data?"
 - o Conservative management without follow up

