1.2.2 Methods

To describe findings during follow up, we will use cumulative incidence curves that reflect the competing risk setting. The follow-up time will be computed in months.

In competing risk survival analysis, the hazard and cumulative incidence of competing (i.e. mutually exclusive) events are estimated over time. The basic competing risk outcome levels reflect the overall study outcome, and are 'surgery performed', 'cyst spontaneously resolved', and 'patient died (for any reason)', whichever comes first. When surgery is performed, this can be further subdivided based on reason for surgery and findings at surgery. For these subdivisions, it is possible that two events (i.e. reasons or findings) occur simultaneously. For example, a patient can undergo surgery due to acute pain and fertility concerns. We therefore specified a hierarchy of the competing events and if two events occur simultaneously, the event highest in the hierarchy is given to the observation. The hierarchies are shown in Box 1. For example, when the patient is operated due to acute pain and fertility concerns, the patient is said to have the event acute pain.

Box 1. Hierarchy of reasons for surgery and findings at surgery.

Reasons for surgery	Findings at surgery
1. Suspicion of malignancy ^a	1. Invasive
2. Pain ^b	2. Borderline
3. Patient request/opportunistic ^c	3. Torsion
	4. Cyst rupture
	5. Minor complications ^d
	6. No complications of tumor

^a Includes ‘suspicion of malignancy based on ultrasound; suspicion of malignancy based on: increase in size, change in morphology, change in vascularity, raised or increase in CA125, raised HE4, CT finding, MRI findings’

^b Includes ‘acute pain (suspected torsion, suspected cyst rupture), chronic pain’

^c Includes ‘fertility concerns, patient request, opportunistic removal’

^d Includes ‘tumor bleeding, adhesions, inflammation/infection’

We will derive cumulative incidence functions for study outcome, reason for surgery, and findings at surgery. For each outcome, figures depicting the cumulative incidence will be produced, as well as tables at time points 12 and 24 months containing the cumulative incidences of the competing events with 95% CI.

Median follow-up will be estimated by the reverse Kaplan-Meier method, i.e. where censoring is denoted as the event, and events denoted as censoring. This is the common method to visualize the censoring function.

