Subgroup analyses will also be performed in the same manner as the overall analysis. Subgroup variables are tumour type (unilocular, unilocular-solid, multilocular, multilocular-solid, solid), presumed diagnosis (see table below), subjective assessment (certainly benign, probably benign), Lesion size (median split method + description on the cumulative incidence at cut-offs 3, 4, 5, 7, 10 cm), and menopausal status. For menopausal status, the data collection software contains a bug such that this information is overwritten by the menopausal status of the last visit. Therefore, for a small group of patients who are labeled postmenopausal, it is possible that they were premenopausal at the first visit in the study. However, we will use the variable as currently available in the dataset. If menopausal status is uncertain, we will classify it as postmenopausal if age at inclusion is 50 or higher.

In all subgroup analyses, we will report cumulative incidences on: spontaneous resolution, death (any cause), surgery (any reason), malignancy, torsion, rupture.

In the subgroup analyses, cumulative incidences will only be reported at 24 months.

Table. Presumed diagnoses at first visit

Presumed diagnosis	N (%)
Simple cyst / para-ovarian or salpingeal cyst/ Serous cystadenoma / serous cystadenofibroma	1470 (47%)
Endometrioma	609 (19%)
Teratoma	325 (10%)
Functional cyst	186 (6%)
Fibroma / fibrothecoma	180 (6%)
Mucinous cystadenoma / mucinous cystadenofibroma	129 (4%)
Hydrosalpinx	122 (4%)

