Table: Cumulative incidence of each outcome (death (any cause), spontaneous resolution, surgery (any reason), malignancy, torsion, rupture at 24 months with 95% CI for all levels of all subgroup variables for patients with new masses. This will be done based on data from patients with newly detected masses only.

Subgroup variable	Death (any cause)	Spontaneous resolution	Surgery (any reason)	Malignancy	Torsion	Rupture
Tumor type						
Unilocular						
Unilocular-solid						
...						
Presumed diagnosis						
Endometriosis						
...						
Subjective assessment						
Certainly benign						
Probably benign						
...						
Lesion size						
median split (4 cm?)						
cut-offs 3, 4, 5, 7, 10 cm						
...						
Menopausal status						
Premenopausal						
Postmenopausal						

Table: For cases with initial policy conservative but who were nevertheless immediately operated: overview of histology at surgery. This will be done based on data from patients with newly detected masses only.

Histology	N (%)
Endometrioma	
Dermoid	
...	
Borderline	
...	

Table: Overview of reasons for surgery for cases with initial policy conservative, stratified by whether they were nevertheless immediately operated or not. This will be done based on data from patients with newly detected masses only.

Reason for surgery	Immediately operated N (%)	Patients with FU N (%)
Suspicion of malignancy		
Pain		
Suspected torsion		
Suspected cyst rupture		
Acute pain		
Chronic pain		
Patient request / opportunistic		
Fertility concerns		
Patient request, other		
Opportunistic		

Table. Sensitivity analysis using data from all centres. This will be done based on data from patients with newly detected masses only.

	12 months	24 months
Study outcome		
Cyst resolution		
Patient died		
Surgery performed		
Reason for surgery		
Suspicion of malignancy		
Pain ^b		
Patient request/opportunistic ^c		
Findings at surgery		
Invasive		
Borderline		
Torsion		
Cyst rupture		
Minor complications		
No complications		

Table. Sensitivity analysis including patients that were immediately operated. This will be done based on data from patients with newly detected masses only.

	12 months	24 months
Study outcome		
Cyst resolution		
Patient died		
Surgery performed		
Reason for surgery		
Suspicion of malignancy		
Pain ^b		
Patient request/opportunistic ^c		
Findings at surgery		
Invasive		
Borderline		
Torsion		
Cyst rupture		
Minor complications		
No complications		

IOTA5 interim analysis

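### The follow-up SAP describes lesion size only by a sample-median split and five loosely defined cut-offs; a continuous size analysis for resolution and surgery would be a cheap improvement

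*SAP*

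**What the plan says.** The protocol records size as a measurement. Under Ultrasound examination, dimensions are taken in mm, including "The lesion in two perpendicular planes", and the list of recorded variables has "Max diameter of lesion".

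The follow-up SAP, section 1.2.2, lists size among the subgroup variables as "Lesion size (median split method + description on the cumulative incidence at cut-offs 3, 4, 5, 7, 10 cm". In section 1.2.3 the subgroup table has two size rows: "median split (4 cm", where the 4 cm carries a question mark, and "cut-offs 3, 4, 5, 7, 10 cm". That table is restricted to newly detected masses and reports 95% confidence intervals.

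The outcomes are set in section 1.2.2: "In all subgroup analyses, we will report cumulative incidences on: spontaneous resolution, death (any cause), surgery (any reason), malignancy, torsion, rupture". The time point is also set there: "In the subgroup analyses, cumulative incidences will only be reported at 24 months". The purpose is descriptive: "To describe findings during follow up, we will use cumulative incidence curves that reflect the competing risk setting". No regression, trend test or other test involving size is planned in this SAP.

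Two other places touch on size. Section 1.2.3 plans a case-by-case table of confirmed malignancies, ruptures and torsions that includes each mass's size at first scan and its change in size. The protocol's Statistical analysis section plans multivariable survival modelling of the need for surgery (objective 3) and longitudinal curves (objective 4), but does not say how size would enter the survival model.

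**The concern.** Size is central to the question. The protocol's introduction frames earlier evidence on conservative management by diameter: dermoids below 6 cm, simple cysts below 5 cm, and uni- or multilocular cysts below 7 cm. A reader of the follow-up report will want to know how the chance of resolution or surgery changes with diameter.

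Three features of the plan limit the answer:

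- The median is a property of the women recruited. Another cohort will have another median, so a risk above or below the median cannot be carried over or built into a management algorithm.
- The five fixed cut-offs are better, but their meaning is left open. Six adjacent bands and five overlapping above/below splits are different tables with different estimates.
- Either way the report gives step values with no curve. Nothing can be read at a size between cut-offs; 6 cm, for example, is named in the introduction but is not among them.

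**Working it through.** The documents give no information, power or sample-size figure for this subgroup, so there is none to reproduce. They also give no distribution of lesion size. Every size distribution below is therefore an assumption, centred on the 4 cm in the table shell and varied around it.

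**Measure.** The information a grouping keeps on a linear trend, for a small effect, is R² = (variance of the group means of size) ÷ (total variance of size). The loss is 1 − R². Using the correct continuous form loses 0 by definition.

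**Median split alone.** For a normal variable the two half-means lie at ±σ√(2/π). So R² = 2/π = 0.637 and the loss is 0.363. This holds for log size if size is log-normal and acts linearly on the log scale. For other cases:

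- Effect linear in cm, log-normal size: loss 41%, 44%, 48% and 53% for log-SD 0.3, 0.4, 0.5 and 0.6.
- Gamma shapes: 39 to 45%. Uniform: 25%.

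**Adjacent bands at 3, 4, 5, 7 and 10 cm.** On the log scale, with z = ln(cut-off/4)/s, R² = Σ[φ(lower z) − φ(upper z)]²/p, where p is the share of women in the band. With median 4 cm and s = 0.5, the cut-offs fall at z = −0.575, 0, 0.446, 1.119 and 1.833:

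| Band (cm) | Share p | Term |
|---|---|---|
| <3 | 0.283 | 0.405 |
| 3–4 | 0.217 | 0.017 |
| 4–5 | 0.172 | 0.008 |
| 5–7 | 0.196 | 0.111 |
| 7–10 | 0.098 | 0.197 |
| ≥10 | 0.033 | 0.166 |

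The terms sum to 0.904, a loss of 9.6%. With median 4 cm and log-SD 0.3 to 0.6, the loss is 8.9 to 10.8% (linear in log size) or 6.7 to 11.7% (linear in cm). Over medians of 3.5, 4 and 5 cm, the full range is about 6 to 17%.

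**What the rows would show.** Assume the same distribution, an overall 24-month risk of 1%, and risk proportional to diameter. Mean size is 4·exp(0.5²/2) = 4.53 cm.

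- True risk at 4 cm: 1% × 4/4.53 = 0.88%. At 10 cm: 1% × 10/4.53 = 2.21%.
- The above-median row shows 1% × 2Φ(0.5) = 1.38%, one figure for that whole range.
- The 4–5, 5–7, 7–10 and ≥10 cm bands show 0.99%, 1.29%, 1.80% and 2.73%, from [Φ(upper z − 0.5) − Φ(lower z − 0.5)]/p. The bands recover the gradient that the median row hides.

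**Precision at large sizes.** With an assumed 2000 women, the ≥10 cm band holds 2000 × 0.0334 ≈ 67 (about 22 to 127 for log-SD 0.4 to 0.6). If it contains no events, and censoring is ignored, the exact 95% upper limit is 1 − 0.025^(1/67) = 5.4% (about 15% with 22 women, 2.9% with 127).

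**The case against.** The strongest defence is that this is a descriptive interim report and that the median split does not stand alone. The fixed cut-offs transfer to other cohorts, and two of them, 5 and 7 cm, match sizes in the protocol's introduction. For malignancy, torsion and rupture, the case table gives the actual size of each mass. Modelling of surgery is assigned to protocol objective 3. Non-parametric estimates by band make no assumption about the shape of the size effect, which matters when events are few. Most of this stands.

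Three stronger readings are tempting, and the documents support none of them:

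- A reader might infer that the plan discards about 36% of the information on size. That figure belongs to a median split alone, with normal size or log size and a linear effect. The plan adds five cut-offs.
- A reader might infer lost power. Where a continuous trend test has 80% power, a median split has Φ(2.802 × √0.637 − 1.96) = 61%. No test of size and no power target is planned, so nothing planned is weakened.
- A reader might infer that all masses above about 4 cm receive a single average risk. That is true of one table row; the cut-offs at 5, 7 and 10 cm describe the same women further.

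The defence leaves some gaps. The split point carries a question mark, and the cut-offs are not defined as bands or splits. The case table has no event-free women for comparison and does not cover resolution, death or surgery in general. Objective 3 does not state how size enters, and it does not cover resolution, torsion or rupture separately.

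**Conclusion.** The point holds as a cheap improvement. It does not show an error that invalidates any planned estimate. The follow-up SAP analyses a continuous measurement only in categories, one of them cut at an unfixed sample median, and leaves the meaning of the others open.

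The size of the loss depends on the reading. It is about 36% for the median split alone under normality and linearity (25 to 53% over the shapes tried), and about 6 to 17% if the cut-offs are adjacent bands and size is log-normal. If they are meant as separate above/below splits, each is a further dichotomy and the band figure does not apply. The practical consequence is a coarse description of how outcome varies with size, probably imprecise for the largest masses. That last part rests on the assumed distribution.

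**What to change.** In section 1.2.2 and the subgroup table of section 1.2.3 of the follow-up SAP:

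1. Delete the median split.
2. State that 3, 4, 5, 7 and 10 cm define six adjacent bands of maximum lesion diameter at first scan, each reported with its non-parametric 24-month cumulative incidence and 95% CI.
3. For newly detected masses, add a cause-specific Cox or Fine-Gray model for spontaneous resolution and another for surgery, with log(diameter) as a restricted cubic spline (3 to 4 knots). Report 24-month cumulative incidence against diameter with its 95% CI. If cause-specific models are used, those for the competing events are needed as well to obtain the cumulative incidence.
4. For malignancy, torsion, rupture and death, keep the non-parametric band estimates, and keep the planned case table for the first three. A single linear log(diameter) term may be shown as supplementary, labelled as resting on log-linearity. It should not replace the band estimates, because with few events a prediction at 10 cm would depend heavily on the assumed form.

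The cost is one paragraph of SAP text and a few model fits on data already collected. The drawback is some model dependence in the added curves, which readers can check against the band estimates beside them.

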1.2.3 Planned analyses, figures, tables

This list does not indicate which figures or tables will be included in the main document.

Figure: Flowchart of patients

Table: Patient and tumor characteristics at inclusion for patients with initial policy conservative (including patients that were operated immediately). *The list of variables to be described can be augmented with other relevant variables according to clinicians, and these will be added irrespective of the results.*

	All patients	Patients with newly detected masses	Patients with masses already in follow-up
Age			
Menopausal status			
Time in follow-up before inclusion		NA	
Tumor type			
Lesion size			
Solid parts			
...			
Presumed diagnosis (endometrioma etc)			
...			
Subjective assessment (certainty)			
Immediately operated			
Patients with a newly detected masses, n (%)		NA	NA
Symptomatic at first scan			
Pain			
Abnormal bleeding			
Other symptoms			
Outcome events			
Cyst spontaneously resolved			
Surgery performed			
Invasive tumor			
Borderline tumor			
Cyst torsion			
Cyst rupture			
Complications detected at surgery*			
No complication detected at surgery			
Patient died			

Table: List of centers, with number of patients per center. This table will include all centers (all the ones included in the sensitivity analysis). Order by total number of patients (conservative and surgery). This table is intended to be included in the appendix or supplementary material.

Center	N	Initial policy surgery	Initial policy conservative	% No info	% Useful info
Malmo, Sweden					
Leuven, Belgium					
Rome, Italy					
...					
All oncology centers					
All non-oncology centers					
All centers					

Useful information: study outcome observed, or follow-up of at least 10 months.

Table: List of centers, with number of patients per center. This table will include centers with sufficient data quality (all the ones included in the primary analysis). Order by total number of patients (conservative). This table is intended to be included in the main report.

Center	Initial policy conservative	% Useful info
Malmo, Sweden		
Leuven, Belgium		
Rome, Italy		
...		
All oncology centers		
All non-oncology centers		
All centers		

Figure: Histogram of time of follow-up before recruitment in IOTA5 for patients with a mass already in follow-up at inclusion ('old' patients)

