1.4 Models to be investigated

The following models will be validated:

- Risk of Malignancy Index (RMI) (Jacobs, 1990)
- IOTA LR2 model (Timmerman, 2005)
- IOTA Simple Rules (Timmerman 2008)
- IOTA Simple Rules Risk model (SRRisks) (Timmerman, 2016)
- IOTA ADNEX model (Van Calster, 2014)
- IOTA ADNEX without CA125 (Van Calster, 2014)

RMI, LR2, and SRRisks predict whether a tumor is malignant (vs benign), with borderline tumors being classified as malignant. ADNEX predicts malignant subgroups. More specifically, it gives 5 probabilities for each patient, for the following outcome categories: benign, borderline, stage I primary invasive, stage II-IV primary invasive, and secondary metastasis. One minus the probability of a benign tumor then equals the probability of malignancy.

In addition, we will also assess the performance of subjective assessment, which is customary in this field. We will assess subjective assessment as a binary judgment (benign vs malignant).

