1.5.7. Subgroup analyses

We will compute the overall c-statistic for benign vs malignancy (i.e. after meta-analysis) and overall calibration curves for the following prespecified subgroups:

- By actual management: separate analysis of patients who were operated within 120 days after the first scan and without follow-up scan (similar to the population for the IOTA1-4 studies), and patients who received at least 1 follow-up scan; note that not all recruited patients fall within one of these two categories
- By suggested management ('intention to treat'): separate analysis of patients with suggested management surgery and patients with suggested management conservative
- By menopausal status: separate analysis of premenopausal patients and postmenopausal patient separately
- By type of center: separate analysis of patients examined in oncology centers and patients examined in other centers

The analysis of these subgroups will be done on data from the main centers, using meta-analysis if numbers allow. If numbers (e.g. number of patients with a malignancy) per center are too small, pooled analysis will be done.

No subgroup analyses are planned for the additional assessment of multinomial discrimination and calibration of the ADNEX model.

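### Menopausal status is known to be overwritten by the last-visit value but is still used as a baseline subgroup, so group membership depends on how long a woman stays in follow-up

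*SAP*

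**What the plan says.** The follow-up SAP, section 1.2.2, states the fault: "For menopausal status, the data collection software contains a bug such that this information is overwritten by the menopausal status of the last visit". It gives the direction and a verbal size: "Therefore, for a small group of patients who are labeled postmenopausal, it is possible that they were premenopausal at the first visit". Its decision is: "However, we will use the variable as currently available in the dataset". An age rule exists, but only for a different problem: "If menopausal status is uncertain, we will classify it as postmenopausal if age at inclusion is 50 or higher".

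The variable is used in two places in that SAP. It is one of five subgroup variables, with cumulative incidence reported at 24 months for women with new masses (sections 1.2.2 and 1.2.3). It is also a row in this table: "Table: Patient and tumor characteristics at inclusion for patients with initial policy conservative". The planned sensitivity analyses add the remaining centres and the immediately operated women. Neither addresses the overwriting.

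The model-performance SAP draws on the same recruitment window and the same cut-off of 30 June 2017 (section 1.2). It plans a subgroup analysis: "By menopausal status: separate analysis of premenopausal patients and postmenopausal patient separately". It also evaluates RMI (sections 1.4 and 1.5.3), which incorporates menopausal status according to the title of the source cited in section 1.6. It does not mention the fault. Section 1.5.1 ties tumour descriptors to the inclusion scan but says nothing about which visit supplies menopausal status.

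**The concern.** A baseline subgroup should be fixed at time zero. Here the label is set at the last visit, which may come well after the 24-month point at which the risk is reported. A woman whose mass resolves or is removed early has little time to change status before her visits end. A woman who stays event-free for years has much more. Relabelling therefore moves women selected for having had no event from the premenopausal to the postmenopausal group. This is immortal-time misclassification, not random noise. By itself it tends to lower event rates in the group labelled postmenopausal and raise them in the group labelled premenopausal, on top of any true difference.

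The SAP recognises this kind of selection elsewhere. Section 1.2.1 treats masses already in follow-up as a selected group and turns to new masses for more correct estimates. The overwritten label brings similar selection back into the new-mass subgroup table.

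At stake are the 24-month risks presented separately for pre- and postmenopausal women and, if the same value feeds the 2019 analyses, the menopausal subgroup and RMI there.

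**Working it through.** The plan gives no number of relabelled women, so there is no figure to reproduce. The check asks how the fault works and what order of size it could have.

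**Inputs from the documents.** Recruitment ran from 1 January 2012 to 1 March 2015, with follow-up to 30 June 2017. Potential follow-up is therefore 28.0 months for the last woman recruited and 65.9 months for the first. Scans are at 3 and 6 months, then every 12 months (protocol, Follow-up). The survival analysis requires at least one follow-up scan (follow-up SAP 1.2.1), so every analysed woman has a later visit that can overwrite her value.

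**Assumptions, not in the documents.** Age distribution and age at menopause are as in the table. Loss is 10% per year, hazards are constant, and there are no visits after an event. Scenarios A-C give both true groups the same 24-month risks (20% resolution, 16% surgery). Scenario D is A with unequal risks (resolution 30% pre, 10% post; surgery 20% pre, 10% post). Each scenario has 600,000 simulated women, with Aalen-Johansen incidence at 24 months.

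**Step 1: relabelling grows with follow-up.** In scenario A the share of truly premenopausal women labelled postmenopausal is 1.0% if the last visit is at 3 months, 4.2% at 12, 8.4% at 24, 12.7% at 36 and 21.0% at 60. In scenario C, which has most women near menopause, it reaches 34.8% at 60 months.

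**Step 2: effect on the subgroup results (pre v post, %).**

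| Scenario: mean age (SD); menopause (SD) | Relabelled, % of followed | Relabelled, % of labelled post | Resolution: true status | Resolution: recorded label | Surgery: true status | Surgery: recorded label |
|---|---|---|---|---|---|---|
| A: 48 (16); 51 (4) | 4.9 | 10.3 | 19.8 v 19.7 | 20.7 v 18.7 | 15.1 v 15.1 | 16.1 v 13.9 |
| B: 45 (12); 51 (4) | 6.0 | 15.9 | 19.9 v 19.8 | 20.8 v 18.3 | 15.1 v 15.1 | 16.2 v 13.3 |
| C: 50 (10); 50 (5) | 7.1 | 12.4 | 19.7 v 19.9 | 21.3 v 18.7 | 15.1 v 15.1 | 17.0 v 13.7 |
| D: as A, unequal risks | 4.2 | 8.9 | 29.6 v 9.9 | 30.5 v 10.7 | 19.1 v 9.2 | 20.2 v 9.0 |

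In A-C, where no true difference exists, the recorded label produces gaps of 1.9-2.7 points for resolution and 2.2-3.3 points for surgery.

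**Step 3: hand check of scenario A, surgery.** Relabelled women have a 24-month surgery incidence of 4.7%, against 15.1% overall. They make up 10.3% of the labelled-postmenopausal group, so that group has about 0.103 × 4.7 + 0.897 × 15.1 = 14.0%. They are 8.6% of the truly premenopausal women, so those left have about (15.1 − 0.086 × 4.7) / 0.914 = 16.1%. The gap is about 2.1 points, against 2.2 simulated.

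**Step 4: alternative groupings.** A further simulation, again with assumed ages and equal true risks, gave a spurious surgery gap of about 2.4-3.5 points with the recorded label. The gap was about 0.8-1.2 points when the age-50 rule was applied only to followed women labelled postmenopausal. It was about zero when all women were grouped by age at inclusion.

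**The case against.** The strongest reply is that the SAP is open about the fault, names its direction and considers the affected group small. Menopausal status is one of five descriptive subgroup variables, reported at one time point, with no planned test of pre against post. The overall cumulative incidences do not use it. All of this stands and limits the consequence. It does not settle the matter, because no count supports the word small and disclosure does not remove a directional error.

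Three stronger readings are tempting and are not supported.

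- A reader might infer that RMI, and hence the model comparison, is shown to be biased. The fault is described only in the 2017 SAP. The 2019 SAP is silent on which value it uses and on whether first-visit status was recovered. The documents do not give the RMI weight for menopausal status, so no shift in sensitivity or specificity can be calculated. What can be said is conditional: if the overwritten value is used, the error can arise only in women with a later visit, so it differs by management.
- A reader might take the direction as certain for every event. It is the effect of relabelling alone. In scenario D the labelled-postmenopausal resolution rate goes up, from 9.9% to 10.7%, because relabelled women bring the higher premenopausal risk with them.
- A reader might contrast followed women with those operated at once. That contrast does not exist in the main follow-up subgroup analysis, which requires a follow-up scan. It matters only for the inclusion table and, conditionally, for the 2019 SAP.

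**Conclusion.** The concern holds for the follow-up SAP. A subgroup reported at 24 months and a row described as an inclusion characteristic rest on a post-baseline value whose error grows with event-free follow-up, and no planned analysis tests this. The real size is unknown. Under the assumed ages, roughly 4-7% of followed women, or 9-16% of those labelled postmenopausal, are relabelled, and the artificial gap with equal true risks is about 2-3 points. These figures show direction and order only. With unequal risks (scenario D) the gap widened by about 0.2 points for resolution and 1.3 for surgery.

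For the 2019 SAP the point is an inference: its menopausal subgroup and RMI carry the same fault unless first-visit status was recovered. The overall cumulative incidences are untouched. This is a cheap improvement to secondary results, not a threat to the main ones.

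**What to change.** 1. Recover first-visit menopausal status from source records or an audit trail, if either exists.
2. In any case, report how many women could be affected: labelled postmenopausal with at least one later visit, tabulated by age at inclusion.
3. Repeat the menopausal subgroup results in both SAPs, and RMI, with all women classified by age at inclusion (below 50, or 50 and over). This is the cut-point the follow-up SAP already uses for uncertain status.
4. State in the model-performance SAP which menopausal value enters the subgroup and RMI.

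The age rule should not be applied only to followed women labelled postmenopausal. In a simulation with similar assumptions, 40-45% of relabelled women were 50 or over at inclusion and stayed uncorrected, while 3.3-5.0% of followed women became newly misclassified. Total misclassification rose in all four scenarios (5.3 to 5.7%, 5.7 to 6.1%, 4.7 to 6.8%, 6.9 to 7.4%). That rule would also treat a woman postmenopausal before 50 differently according to whether she was followed or operated at once, which is a new management-dependent error.

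The cost is one derived variable from age at inclusion, which is already in the planned tables. The downside is that age 50 is an imperfect proxy. It misclassifies more women overall, although not in a way that depends on follow-up, so it should be shown beside the as-recorded result and not in place of it.
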